11.1 Assessments for Safety Evaluations

- 1) Adverse events
 - a) Symptoms and signs
 - b) Abnormal laboratory test values
 - c) Abnormal vital signs
 - d) Abnormal electrocardiograms
- 2) Laboratory test values
- 3) Vital signs
- 4) Electrocardiograms
- 5) Echocardiography

11.2 Definition of Adverse Events

- 1) Adverse events (AEs)

An AE in the study will be defined as any undesirable or unexpected sign, symptom, disease, or aggravation of an existing condition occurring in a participant who is given an IP on or after the time of informed consent regardless of whether there is a causal relationship to the IP. The aggravation of diseases or symptoms that have occurred before the time of informed consent are also considered an AE.

The following events are not considered AE:

- Events for which medical treatment had been scheduled before the time of informed consent
- Aggravation of primary disease

- 2) Serious adverse events (SAEs)

- a) Results in death
- b) Is life-threatening
- c) Requires or prolongs inpatient hospitalization*

*Excluding the following events;

- Any hospitalization that had been scheduled before the time of informed consent (e.g., hospitalization for surgeries and detailed examinations)
- Any hospitalization for examinations without any treatment (including bed rest treatment).

- d) Results in persistent or significant disability/incapacity
- e) Is a congenital anomaly/birth defect
- f) Is another medically important condition*

*An important medical event that may not be immediately life-threatening or does not result in death or hospitalization but may jeopardize the safety of the patient or may require treatments to prevent one of the other outcomes listed in a) to e) above.

e.g., bronchospasm requiring intensive care at an emergency room, blood dyscrasias or convulsions not leading to hospitalization, drug dependence, or drug abuse

- 3) Adverse events of special interest (AESIs)

AESIs in this study are defined as the following treatment-emergent events:

- a) AEs requiring discontinuation of study treatment

- b) Injection-related reactions (including local and systemic injection site reactions)
Injection-related reactions are defined as AEs which develop within 24 hours after administration of IP.
- c) Asthma
- d) Atopic dermatitis
- e) Skin symptoms with edematous erythema or scales
- f) Skin infections
- g) Non-skin infections
- h) Suspected infection of infectious pathogen from the IP

• Rationale for selection

b), c), d), f), and g)	These events should be monitored carefully because of being included in “important potential risks” in nemolizumab.
e)	These are events of interest closely monitored by the sponsor based on the results of clinical studies of nemolizumab in patients with atopic dermatitis
h)	The event should be carefully investigated in biological products in general.

11.3 Definitions of Safety Endpoints

1) Adverse events

a) Symptoms and signs

The investigator or subinvestigator will assess symptoms and signs in participants after the time of informed consent through the time of physical examination on the day of follow-up visit based on interview results and complaints from participants.

b) Abnormal laboratory test values

The investigator or subinvestigator will treat laboratory test results collected after the time of informed consent through the day of follow-up visit as AEs if the results meet any of the following criteria:

- i. Accompanied with clinical symptoms
- ii. Resulted in any change of study treatment (e.g., interruption or discontinuation of the IP).
- iii. Resulted in medical treatment (including change of concomitant medications/therapies).
- iv. Considered clinically significant by the investigator or subinvestigator.
- v. Total bilirubin is >2-fold the upper limit of the reference value, and ALT or AST is >3-fold the upper limit of the reference value
- vi. ALT or AST is >3-fold the upper limit of the reference value with clinical jaundice

Individual abnormal changes in laboratory test findings will be reported as individual AEs in principle. However, a single abnormal laboratory test finding or two or more abnormal laboratory test findings that are related to each other may be reported collectively as a single event under a single diagnosis if it is considered appropriate by the investigator or sub-investigator. If individual abnormal changes in laboratory test findings are regarded by the investigator or subinvestigator as manifestations of a symptom or a sign reported as an AE, the changes may be reported collectively with the AE of the symptom or sign.

Laboratory values may change depending on interindividual factors, such as sex, age, and lifestyle, and intraindividual factors, such as diurnal fluctuation, diet, exercise, body positioning, and sexual cycle. Therefore, the investigator or subinvestigator will determine whether the change in each laboratory test findings is a physiological change or an abnormal change after sufficiently taking into

consideration the demographics of each participant, such as the underlying disease and complication, baseline values, and the changes specific to each participant who have any periodic laboratory test before study participation.

c) Abnormal vital signs

The investigator or subinvestigator will treat measurement results collected after the time of informed consent through the day of follow-up visit as AEs if the results meet any of the following criteria:

- i. Accompanied with clinical symptoms
- ii. Resulted in any change of study treatment (e.g., interruption or discontinuation of the IP).
- iii. Resulted in medical treatment (including change of concomitant medications/therapies).
- iv. Considered clinically significant by the investigator or subinvestigator.

d) Abnormal electrocardiograms

The investigator or subinvestigator will assess AEs based on the results collected after the time of informed consent through the day of follow-up visit

e) Echocardiography

Echocardiographic images will be assessed for cardiac morphology, cardiac motion and blood flow during cardiac contraction and relaxation, and other parameters. The investigator or subinvestigator will record the presence or absence of abnormalities in the source documents.

11.4 Review and reporting of adverse events

The investigator or subinvestigator will assess the items shown in [Table 11-1](#) regarding AEs occurring from after obtaining informed consent to the day of follow-up visit and fill the necessary information in the case report forms (CRFs).

The investigator or subinvestigator will report the SAEs according to [Section 11.5](#) and the AESIs according to [Section 11.6](#) to the sponsor. The investigator or subinvestigator will promptly report the other AEs to the sponsor.

Table 11-1 Assessments for adverse events

Assessments	Details of assessment	
Name of adverse event	Disease name/symptom, classification of the site of occurrence of adverse events	
Onset date	Classification of onset date, Onset date	
Action on investigational product	Treatment discontinuation, Treatment interruption, Dose reduction, No dose change, Not applicable, Unknown	
Treatment for the event	Presence or absence of treatment	
Outcomes and Date of outcome/Date of outcome obtained	Recovered/Resolved, Recovering/Resolving, Not Recovered/Not Resolved, Recovered/Resolved with sequelae, Death, and Unknown End date of AE, whether the AE is ongoing or not	
Severity	Mild	Transient, requiring minimal treatment and not interfering with daily life
	Moderate	Specified treatments relieve symptoms and do not result in permanent or significant disability but interfere with daily life
	Severe	Significant effect on advanced clinical condition or requiring intensive care or no longer allowing daily life.
Seriousness	Serious/Non-serious	
Definition of serious adverse events in Section 13.2	1. Results in death	
	2. Life-threatening	
	3. Requires or prolongs inpatient hospitalization	
	4. Results in persistent or significant disability/incapacity	
	5. Is a congenital anomaly/birth defect	
	6. Is another medically important condition	
Causal relationship with investigational product	Causality classification (according to the following causality classification), and rationale	
Causality classification*	Not related	Causal relationship is unlikely because the adverse event has no plausible temporal relationship to administration of IP, or the event can be explained by another factor. The rationale for no causal relationship is required to be described.
	Related	Causal relationship is presumed because there is a plausible temporal relationship between the onset of the adverse event and administration of investigational drug, and the event cannot be readily explained by another factor. The rationale for the causal relationship should be described if it is necessary to be explained.

*The following guidance can be taken into consideration on causality assessment: resolution of the event after discontinuation of IP; recurrence after restarting of IP; established causal relationship with IP or similar drugs; no confounding risk factors; consistency with the amount and duration of exposure to IP; almost clearly explainable involvement of the IP based on the correct past medical history; no reasonable possibility of causal relationship with concomitant therapy, etc.

11.5 Review and reporting of serious adverse events

- 1) The investigator will report any serious adverse events to the sponsor within 24 hours of getting to know the occurrence of the event. The investigator will report detailed information to the sponsor by using the “Report of Serious Adverse Events” form within 2 days of getting to know the occurrence of the event (the date the event was known is regarded as day 0). The study site’s own form may be used instead of the "Report of Serious Adverse Events". For additional reporting, new serious information (e.g., change in the name of the adverse event, causal relationship, outcome information, the severity category, etc.) should be reported to the sponsor according to the above rules when it becomes known.
- 2) The investigator will report the event to the study site according to the study site’s operating procedures.
- 3) The investigator will provide any additional information (e.g., autopsy reports, late-stage medical records, and other necessary information) on reported serious adverse events, as requested by the sponsor.

11.6 Reporting of adverse events of special interests (AESIs)

The investigator should report to the sponsor promptly when an AESI is noted. For atopic dermatitis and skin symptoms with edematous erythema or scaling, the necessary information (details of the symptoms/signs and the basis for determining the causal relationship with the IP) should be stated in the CRF. Any additional information should be provided, as requested by the sponsor.

At the time of physical examination on the day of follow-up visit, the final outcome of any AESI “not recovered/not resolved” falling under 1) below should be obtained according to 2). Concomitant medications and therapies will also be collected according to Sections [9.3.2.1](#) and [9.3.2.2](#).

- 1) AESIs to be obtained
 - a) AEs requiring discontinuation of study treatment
 - b) Asthma
 - c) Atopic dermatitis
 - d) Skin symptoms with edematous erythema or scales
- 2) Period to obtain AESIs

AESIs should be collected until the earlier of the following dates to obtain the final outcome information (the outcome and the date of outcome/outcome obtained).

 - Date of recovering or recovered
 - Date 6 months after the last dose of IP

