11.10 Follow-up of Adverse Events

For all adverse events developing during the study period (from the time of informed consent to the day of follow-up visit), the investigator or subinvestigator will provide appropriate treatments, and follow up until the event recovers to normal condition (within the reference ranges for laboratory test values), to the level before the consent was obtained, or until the investigator or subinvestigator considers that medical follow-up is no longer required. However, AESIs defined in Section 11.6 1) should be obtained according to Section 11.6 even if the investigator or subinvestigator considers that their follow-up is not medically necessary.

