19.1.1 Participants assigned to treatment

- 1) Date of written informed consent
- 2) Visit dates
- 3) Participant demographics
- 4) Major therapies received for SSc in the past
- 5) Inclusion and exclusion criteria
- 6) Complications
- 7) Concomitant Medications/Concomitant Therapies
- 8) Patient-reported Outcomes
- 9) Global improvement rating
- 10) mRSS
- 11) The number of digital ulcers
- 12) Respiratory function test
- 13) Electrocardiogram
- 14) Echocardiography
- 15) HRCT
- 16) Severity of pulmonary lesions
- 17) ACR-CRISS
- 18) Vital signs
- 19) Body weight
- 20) Laboratory tests
- 21) Biomarkers
- 22) Serum nemolizumab levels
- 23) Immunogenicity measurement
- 24) Comprehensive measurements of autoantibodies
- 25) CyTOF measurement
- 26) Dosing status of IP
- 27) Adverse events

Information on outcome of an adverse event is to be collected until the follow-up visit.

- 28) The details of adverse events of atopic dermatitis and skin symptoms with edematous erythema or

scaling as well as the basis for determining the causal relationship with the IP

- 29) Malfunction of DCS
- 30) Status of study entry after screening, enrollment, completion/discontinuation of the study
completion status of study entry after screening, completion status of enrollment, study completion status, date of completion, date and reason for discontinuation if discontinued, and impact of COVID-19
- 31) Follow-up visit
Whether there was a follow-up visit or not, date of follow-up visit, date of determination and reason if no follow-up visit, and impact of COVID-19
- 32) Others
 - a) Comment on each assessment
 - b) Unscheduled visits

19.1.2 Participants Who Discontinue the Study before study entry after screening and those Who Discontinue the Study before enrollment

The following data will be collected and documented in the CRF for respective participants:

- 1) to 6) for participants having discontinued the study before study entry after screening
- 1) to 6) and 7) to 16) for participants having discontinued the study before enrollment
- 1) Date of written informed consent
- 2) Visit dates
- 3) Participant demographics
- 4) Inclusion and exclusion criteria
- 5) Adverse events
- 6) Date of and reason for discontinuation
- 7) mRSS
- 8) The number of digital ulcers
- 9) Respiratory function test
- 10) Vital signs
- 11) Body weight
- 12) Severity of pulmonary lesions
- 13) HRCT
- 14) Echocardiography
- 15) Electrocardiograms
- 16) Laboratory tests

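### For the listed AESIs still open at the follow-up visit, mandated outcome collection can end at recovering, and events already recovering at that visit get no extension

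*Combined protocol and SAP*

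**What the plan says.** The text of Section 11.6 is the same in all three protocol copies in the file. The copy with the study period to November 2024 appears to be the current one.

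- **Trigger (11.6).** At the follow-up visit, the final outcome is to be pursued for AESIs graded not recovered/not resolved that are on list 1). The list is: "a) AEs requiring discontinuation of study treatment", then asthma, atopic dermatitis, and skin symptoms with oedematous erythema or scales.
- **End of collection (11.6 2)).** "AESIs should be collected until the earlier of the following dates to obtain the final outcome information". The two dates are "Date of recovering or recovered" and "Date 6 months after the last dose of IP".
- **Outcome scale (Table 11-1 in 11.4).** "Recovered/Resolved, Recovering/Resolving, Not Recovered/Not Resolved, Recovered/Resolved with sequelae, Death, and Unknown".
- **Clinical follow-up (11.10).** For every adverse event the investigator is to "follow up until the event recovers to normal condition (within the reference ranges for laboratory test values"), or to the pre-consent level, or until the investigator judges that follow-up is no longer needed. For the events on list 1), Section 11.6 applies even where the investigator sees no medical need.
- **CRF (19.1.1, item 27).** "Information on outcome of an adverse event is to be collected until the follow-up visit".
- **After the follow-up visit (Section 20).** A separate report carries outcome, drugs and therapies, but only for list 1) events that are not recovered/not resolved at that visit.

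**The concern.** The stated aim of 11.6 is a final outcome, but its first stop date is met by improvement alone. The protocol's own scale separates improvement from resolution. If an asthma or dermatitis event improves after the follow-up visit and then stalls or relapses, the last mandated record shows it improving.

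The trigger has the same weakness. An event that is improving but unresolved at the follow-up visit is treated as if it needed no further outcome.

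At stake is the completeness of the safety record for events the protocol has singled out. Section 11.2 says of asthma and atopic dermatitis, among others, that "These events should be monitored carefully because of being included in" the important potential risks of the drug. Resolution after stopping the drug is also one of the points Table 11-1 offers for judging causality. No endpoint, analysis set or incidence table depends on it.

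**Working it through.** **1. Timing (inputs: half-life 12.6 to 14.6 days, Section 8.3; follow-up visit at 84 ± 7 days, Section 9.2.8; cap of 6 months, Section 11.6, taken as 182 to 183 days).**

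Section 8.3 equates the visit with five half-lives:
- 5 × 12.6 = 63.0 days and 5 × 14.6 = 73.0 days, so day 84 lies beyond five half-lives.
- 84 / 14.6 = 5.75 and 84 / 12.6 = 6.67 half-lives.
- Assuming first-order decline, the residual is 0.5^5.75 = 1.9% to 0.5^6.67 = 1.0% of the last dose.

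Extension available between visit and cap:
- 182 − 84 = 98 days.
- With the visit window, 182 − 91 = 91 days to 183 − 77 = 106 days.

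**2. What the rules yield for a list 1) event, by its course.**

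| Status at follow-up visit | Later course | What is mandated | Gap |
|---|---|---|---|
| Recovered | – | Outcome in CRF | None |
| Not recovered | First recorded improvement is recovered | Recovery date via 11.6 and Section 20 | None |
| Not recovered | No improvement | Status at the 6-month cap | None within the cap |
| Not recovered | Recovering first, then resolves, stalls or relapses | Collection ends at recovering | Remainder of the window |
| Recovering | Any | No extension | Whole window, about 98 days |

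To illustrate the fourth row, suppose the event is graded recovering on day 100 (an assumed day). Collection may then stop with 182 − 100 = 82 days of the window unused. An event showing no improvement is followed to the cap, while one showing partial improvement is not.

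**3. Whether another route fills the gap.**

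- *CRF:* outcome capture ends at the follow-up visit (19.1.1, item 27).
- *New adverse event:* Section 11.4 records events up to the day of the follow-up visit, so a later relapse is not entered as a new event.
- *Section 20:* it has the same trigger as 11.6.
- *Section 11.10:* clinical follow-up continues, but the investigator may end it, and neither the CRF nor Section 20 provides for its result in these two cases.
- *Section 11.5:* new outcome information on serious events is reported when known, with no end date. This covers serious events only.
- *Section 11.6, opening paragraph:* the sponsor may request additional information. This is discretionary.

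The gap is therefore the last two rows of the table, for non-serious events.

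**4. Knock-on effect.** Sections 9.3.2.1 and 9.3.5.4 tie the record of medication for these AESIs, and the closing skin photograph, to the final outcome evaluation. If that evaluation is the date on which 11.6 collection ends, both also stop at recovering.

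**The case against.** The strongest reply is that 11.6 is a minimum added to 11.10, not a replacement for it. Every adverse event stays under clinical follow-up, so no event is clinically closed merely because 11.6 collection stops. Table 11-1 does not label any grade final or non-final, and a sponsor may choose recovering as its endpoint for extended collection in a descriptive study of 8 participants. The first part stands: this is a matter of data capture, not of patient care. The second stands only in part, because 11.6 itself names the final outcome as its aim and the scale keeps recovering apart from recovered.

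A reader might also infer four stronger points, which the documents do not support:

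- *That infections are outside the rule.* An infection that stops treatment falls under list item a), serious infections are reported under 11.5, and all infections are followed under 11.10. Counting the risk categories not named on the list would overlook these routes.
- *That an infection open at the follow-up visit has no outcome.* Its status at that visit is recorded on the Table 11-1 scale. What is missing is a specified route for a later outcome, and only where the infection is non-serious and did not stop treatment.
- *That the trial cannot show whether these risks resolve off drug.* By day 84, 5.75 to 6.67 half-lives have passed, so most washout is observed under full collection before the extension begins.
- *That outcomes enter no planned table.* Section 17.3.3 lists none, but Section 17 gives only the major plans and refers to a separate Statistical Analysis Plan for detail.

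**Conclusion.** The point holds as a gap in data capture. For non-serious AESIs on the 11.6 list, mandated collection after the follow-up visit may stop at recovering, and events already recovering at that visit are left out. Later relapse or non-resolution then has no mandated route into the trial data.

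Its size is up to about 98 days of unused follow-up per event (91 to 106 days over the visit window and the two readings of 6 months). The documents give no expected number of such events; it may be zero. No efficacy result, sample-size figure or adverse event incidence changes. The conclusion rests on reading the 11.6 stop date and trigger literally, and on Section 20 being the only non-serious outcome route after the follow-up visit.

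This is a worthwhile, low-cost improvement rather than an error that threatens the trial's conclusions.

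**What to change.** In Section 11.6, and in Section 20 to match:

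1. Apply the rule to listed AESIs that are either not recovered/not resolved or recovering/resolving at the follow-up visit.
2. End collection at recovered, recovered with sequelae or death, and otherwise at the existing cap of 6 months after the last dose.

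The cost is wording in two sections, the matching report format, and a few extra follow-up contacts in at most 8 participants. Nothing runs past the cap already set, and treatment is unaffected.

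Optional and minor: non-serious infections that did not stop treatment have no specified outcome route after the follow-up visit. The sponsor may consider adding categories f) and g) of Section 11.2 to the 11.6 list, at the price of slightly longer outcome collection for open infections.

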11.7 Photography

Among AESIs, "atopic dermatitis" and "skin symptoms with edematous erythema or scales" will be photographed to examine the detailed skin findings of the events. Other adverse events of which the principal investigator or subinvestigator considers it necessary to take photographs will also be photographed.

The photographs taken will be used as a record of the occurrence of adverse event and a reference for safety evaluation.

